#### 5.7 Withdrawal of individual subjects

Subjects can leave the study at any time for any reason if they wish to do so without any consequences. The attending physician can decide to withdraw a subject from the study for urgent medical reasons.

# 5.8 Replacement of individual subjects after withdrawal

When parents or caregivers want to withdraw their infant for any reason, another infant will be included in the study.

# 5.9 Cost-effectiveness

By calculating the costs of the intervention (EPO treatment), and taking into account

caregiver time and other services needed and the costs of top-up transfusions, we will assess the cost-effectiveness of the intervention compared to the standard of care. The total costs of EPO treatment using darbepoetin alfa are approximately 32 Euro (total of 8 vials of darbepoetin) per child. The costs of a clinical admission at a day-care-center for one top-up transfusion are approximately 700 Euros. An effective treatment with EPO will reduce the average rate of top-up transfusions from an average of 2 top-up transfusions per child to an average of 1 top-up transfusion per child (absolute reduction of 50%), hereby reducing the costs of treatment by almost 50%, from 1400 Euros (without EPO treatment) to 732 Euros (with EPO).

#### 5.10 Statistical analysis

Both intention to treat and per protocol analysis will be carried out to study the differences in outcome measures between the intervention and control group. Intention to treat analysis is our primary choice of analysis. A minimal treatment with 5 out of 8 darbepoetin injections is defined as acceptable protocol deviation. A p-value < 0.05 will be considered to indicate statistical significance. The number of top-up transfusions per infant and, the number of days of admission for top-up transfusions will be compared between both groups using a Mann-Whitney U test. The time from birth to top-up transfusion will be compared between both groups using survival analysis and a log rank test. The percentage of infants requiring a top-up transfusion up to 2 months of life, the percentage of infants with a high blood pressure and the percentage of infants with high ferritin levels will be compared between both groups using  $\chi^2$  tests. If despite randomization the groups differ at baseline in type of alloimmunization, EPO-levels at birth or treatment with exchange transfusion, a multivariable model may be used in a secondary analysis to correct for these factors.

#### 6. REQUIRED CLINICAL EVALUATION

#### 6.1 Maternal and fetal baseline characteristics

The following variables will be recorded: type of red blood cell alloimmunization, course and level of antibody-titers and ADCC (antibody-dependent cell-mediated cytotoxicity test) during pregnancy, number of IUTs, fetal hemoglobin values at start of each IUT, presence of severe fetal anemia (< 5 SD), presence of fetal hydrops.

#### 6.2 Neonatal baseline characteristics

The following variables will be recorded: birth weight, gestational age at birth, gender, Apgar score at 5 min, respiratory distress syndrome, patent ductus arteriosus, necrotizing enterocolitis, sepsis and cerebral lesions on cranial ultrasound examination, number of days of phototherapy, number of exchange transfusions, and highest bilirubin level during admission. At birth, the following measurements will be performed in umbilical cord blood as part of standard care: hemoglobin level, hematocrit, reticulocyte count, nucleated red cells (erythroblasts), iron tests (including serum iron, total iron binding capacity, transferrin and ferritin), liver enzymes (ASAT, ALAT, γGT and LDH). Additionally, EPO-levels will be measured in umbilical cord blood.

#### 6.3 Measurements during follow-up

Complete blood counts including hemoglobin level and reticulocyte count are determined weekly in both groups (standard practice). The number of top-up transfusions received during the first 3 months of life and hemoglobin levels prior to the top-up transfusion are recorded. Iron tests (serum iron, ferritin, transferrin and total iron binding capacity) and liver enzymes (ASAT, ALAT, YGT and LDH) will be determined monthly (standard practice). Blood pressure will be measured at the start of treatment, after four weeks and after eight weeks of treatment.

#### 7. INVESTIGATIONAL PRODUCT

#### 7.1 Name and description of investigational product

In this study, the investigational medicinal product is darbepoetin alfa (Aranesp). Darbepoetin alfa is a long-acting synthetic substitute for the endogenous hormone erythropoietin that stimulates erythropoiesis. A detailed description of darbepoetin alfa can be found in the summary of product characteristics (SPC) which is added to this protocol as a separate document. The authorized indications of darbepoetin alfa are listed in the SPC on page 5. In children, darbepoetin alfa is used as treatment for symptomatic anemia caused by chronic kidney disease. Relevant information on darbepoetin alfa to treat anemia specifically caused by red cell alloimmunization, is provided in this section. Information is provided on both the erythropoietic and neuroprotective aspects of darbepoetin alfa, as neurodevelopmental outcome will be assessed as a secondary end point.

#### 7.2 Summary of findings from non-clinical studies

Erythropoietic: animal studies in rats and dogs showed a marked increase in hemoglobulin levels, hematocrit and reticulocytes after administration of darbepoetin alfa. Adverse effects at high dosages were related to an increased pharmacological effect (decreased tissue perfusion due to increased blood viscosity). Darbepoetin alfa showed no genotoxic or carcinogenic potential, nor had any effect on the proliferation of non-hematological cells *in vitro* or *in vivo* (SPC page 20).

Neuroprotective: both *in vitro* and *in vivo* studies in animal models revealed neuroprotective effects of exogenous EPO administration. These studies showed overall an anti-inflammatory role of EPO and a marked decrease in apoptosis and an increase in neuroregeneration after EPO administration (both recombinant human EPO as well as the long-acting variant darboepoetin alfa) (SPC page 20). Animal studies showed EPO to be able to penetrate the blood brain barrier and showed neuroprotective effects in animal models for neonatal

hypoxic-ischemia and neonatal strokes. A recent study in rats showed neuroprotective effects of EPO (administration of 5000  $\mu$ g/kg) in induced hemolytic hyperbilirubinemia.

#### 7.3 Summary of findings from clinical studies

Erythropoietic: although HDFN is not a registered indication for darbepoetin treatment, offlabel use of medication is common in neonatology. The potential effect of EPO in neonates with HDFN was shown in small studies and casuistic reports, showing overall an increased hemoglobulin level and decreased transfusion need. No severe adverse effects were reported (dosages 200-400  $\mu$ g/kg three times a week, recombinant EPO; correlating to a darbepoetin dosage of 5-10  $\mu$ g/kg once a week).

Systematic reviews of both early (27 randomized controlled trials) and late administration (30 randomized controlled trials) of EPO in preterm infants have shown an overall reduction in RBC transfusions. The rates for mortality and morbidities including intraventricular haemorrhage and necrotizing enterocolitis were not significantly changed, EPO administration showed a trend in increased risk for retinopathy of prematurity in this population. A meta-analysis specifically addressing this issue showed no increased risk for any stage of retinopathy of prematurity. EPO has been shown to protect developing retinas in sheep models of endotoxin induced retinal injury and exogenous EPO was found to improve retinal neuronal function in the early stages of retinopathy. The previous reported increased risk of retinopathy of prematurity after EPO administration was attributed to the effect of excessive levels of iron, which is toxic to tissues and can cause oxidative damage to lipids, proteins, and DNA.

Other potential adverse effects include local skin reactions (pain and erythema) due to subcutaneous administration, increased blood pressure with rarely convulsions and hypersensitivity reactions (SPC page 14).

Neuroprotective: the short-term and long-term neuroprotective effects of EPO and specifically of darbepoetin alfa are most widely studied in preterm neonates and term neonates with hypoxic-ischemic encephalopathy. Darbepoetin alfa showed promising results in these groups compared to placebo and appears to be safe (dosage 10 µg/kg once a week).

#### 7.4 Summary of known and potential risks and benefits

Darbepoetin alfa is registered as treatment of symptomatic anemia due to chronic kidney disease. As such, it is known that darbepoetin potentially causes local skin reactions, increased blood pressure with rarely convulsions and hypersensitivity reactions. Despite these potential risks, darbepoetin alfa can increase hemoglobulin levels and thereby prevent or reduce the amount of top-up transfusions. Potential adverse effects of transfusions would be avoided and the number of days of hospitalization could be reduced. EPO may have an additional beneficial effect on long-term neurodevelopment.

#### 7.5 Description and justification of route of administration and dosage

Darbepoetin alfa is administered subcutaneously, as is common in the registered indications. A dosage of 10 µg/kg once a week for a consecutive period of 8 weeks will be given. The optimal dose of darbepoetin is currently unknown, but the chosen dosage of 10 µg/kg is in agreement with previous studies. A lower dosage is used in anemic patients with chronic kidney disease (SMPC), supporting the probable effectiveness of this dosage to enhance erythropoiesis. When used for its neuroprotective potential, higher dosages are common and are safely used to achieve adequate levels of darbepoetin to pass the blood-brain barrier.

#### 7.6 Preparation and labelling of Investigational Medicinal Product

Preparation and labelling will be done according to relevant GMP guidelines.

Darbepoetin alfa will be provided by the Department of Clinical Pharmacology and

Toxicology of the LUMC.

# 7.7 Drug accountability

Drug accountability will follow current GMP guidelines. The LUMC pharmacy will take full responsibility and supervision of the drug accountability process.

#### 8. SAFETY REPORTING

#### 8.1 Section 10 WMO event

In accordance to section 10, subsection 1, of the WMO, the investigator will inform the parents of the subjects and the accredited METC if anything occurs, on the basis of which it appears that the disadvantages of participation may be significantly greater than was foreseen in the research proposal. The study will be suspended pending further review by the accredited METC, except insofar as suspension would jeopardize the subjects' health. The investigator will take care that all parents of the subjects are kept informed.

#### 8.2 AEs, SAEs and SUSARs

#### 8.2.1 Adverse and serious adverse events (SAEs)

Adverse events are defined as any undesirable experience occurring to a patient during a clinical trial, whether or not considered related to the investigational drug. All adverse events reported spontaneously by the patient's parents or caregivers or observed by the investigator or his staff will be recorded. Serious adverse events are those which result in:

- Death
- A life-threatening event (i.e. an immediate risk of death)
- Hospitalization or prolongation of hospitalization;
- Severe/permanent disability.

During protocol treatment, all deaths, all SAE's that are life-threatening and any unexpected SAE must be reported to the study coordinator within 48 hours of the initial observation of the event. All details should be documented on the serious adverse event and death report and signed by the responsible investigator or one of the authorized staff members. In circumstances where it is not possible to submit a complete report an initial report may be made giving only the mandatory information.

The investigator will decide whether the SAE is related to the treatment (i.e. unrelated, unlikely, possible, probable, definitely and not assessable) and the decision will be recorded on the serious adverse event form. The assessment of causality is made by the investigator using the following criteria:

Relationship	Description
Unrelated	There is no evidence of any causal relationship
Unlikely	There is little evidence to suggest there is a causal relationship (e.g. the
	event did not occur within a reasonable time after administration of the trial
	medication). There is another reasonable explanation for the event.
Possible	There is some evidence to suggest a causal relationship (e.g. the event
	occurred within a reasonable time after administration of the trial medication),
	but other factors may have contributed to the event (e.g. the patients clinical
	condition, other concomitant treatments).
Probable	There is evidence to suggest a causal relationship and the influence of other
	factors is unlikely.
Definitely	There is clear evidence to suggest a causal relationship and other
	contributing factors can be ruled out.
Not	There is insufficient or incomplete evidence to make a clinical judgment of the
assessable	causal relationship.

The investigator will report all SAEs to the sponsor without undue delay after obtaining knowledge of the events. The sponsor will report the SAEs through the web portal *ToetsingOnline* to the accredited METC that approved the protocol, within 7 of first knowledge for SAEs that result in death or are life threatening followed by a period of maximum 8 days to complete the initial preliminary report. All other SAEs will be reported within a period of maximum 15 days after the sponsor has first knowledge of the serious adverse events.

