# 5.2 Study design

Randomized controlled trial. Included neonates will be randomized at birth to treatment with EPO (intervention group) or "standard of care", 1:1 allocation. In the treatment group, EPO (darbepoetin alfa) is administered subcutaneously at a dosage of 10 µg/kg once a week, starting at day 7, for a period of 8 weeks. Treatment is administered during weekly home visits after discharge from the LUMC. Concomitant therapy with folate (0.25 mg/day) is given

in both groups (standard practice). Concomitant iron therapy is given if ferritin level drops below 75 microg/l. Weekly routine measurements of complete blood counts (including hemoglobin level, hematocrit and reticulocyte count) will be performed in both groups (standard practice). EPO is discontinued if hemoglobin level is  $\geq$  13 g/dL after at least 4 weeks of treatment with EPO. Blood pressure will be measured at the start of treatment, after four weeks and after eight weeks. Monthly measurements of liver enzymes (aspartate aminotransferase (ASAT), alanine aminotransferase (ALAT), gamma-glutamyl transferase ( $\gamma$ GT) and lactate dehydrogenase (LDH)) will also be performed in all groups (standard practice). In addition, the neonatal EPO-level will be determined at the start of the treatment with EPO. The number of top-up transfusions received during the first 3 months of life and hemoglobin levels prior to the top-up transfusion are recorded. After initial discharge from the LUMC, top-up transfusions are performed when hemoglobin levels fall below 7.2 g/dL or when hemoglobin is between 7.2 and 8.8 g/dL if clinical symptoms of anemia (lethargy, feeding difficulties or failure to thrive) are present.

At two years of age a physical and neurological examination and an assessment of cognitive and neurological development using the Dutch version of the Bayley Scales of Infant Development, third edition (BSID-III) will be performed (standard practice). BSID-III scores provide mental developmental indexes (MDI) and psychomotor development indexes (PDI).

[figure not shown]

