# 8.2.2 Suspected unexpected serious adverse reactions (SUSARs)

Adverse reactions are all untoward and unintended responses to an investigational product related to any dose administered.

Unexpected adverse reactions are SUSARs if the following three conditions are met:

- 1. the event must be serious (see chapter 8.2.1);
- there must be a certain degree of probability that the event is a harmful and an undesirable reaction to the medicinal product under investigation, regardless of the administered dose;
- 3. the adverse reaction must be unexpected, that is to say, the nature and severity of the adverse reaction are not in agreement with the product information as recorded in the Investigator's Brochure for an unapproved IMP or Summary of Product Characteristics (SPC) for an authorized medicinal product.

The sponsor will report expedited the following SUSARs through the web portal *ToetsingOnline* to the METC:

- SUSARs that have arisen in the clinical trial that was assessed by the METC;
- SUSARs that have arisen in other clinical trials of the same sponsor and with the same medicinal product, and that could have consequences for the safety of the subjects involved in the clinical trial that was assessed by the METC.

The remaining SUSARs are recorded in an overview list (line-listing) that will be submitted once every half year to the METC. This line-listing provides an overview of all SUSARs from the study medicine, accompanied by a brief report highlighting the main points of concern. The expedited reporting of SUSARs through the web portal *ToetsingOnline* is sufficient as notification to the competent authority.

The sponsor will report expedited all SUSARs to the competent authorities in other Member States, according to the requirements of the Member States.

The expedited reporting will occur not later than 15 days after the sponsor has first knowledge of the adverse reactions. For fatal or life threatening cases the term will be maximal 7 days for a preliminary report with another 8 days for completion of the report.

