# 8.3 Annual safety report

In addition to the expedited reporting of SUSARs, the sponsor will submit, once a year throughout the clinical trial, a safety report to the accredited METC, competent authority, and competent authorities of the concerned Member States. This safety report consists of:

- a list of all suspected (unexpected or expected) serious adverse reactions, along with an aggregated summary table of all reported serious adverse reactions, ordered by organ system, per study;
- a report concerning the safety of the subjects, consisting of a complete safety analysis and an evaluation of the balance between the efficacy and the harmfulness of the medicine under investigation.

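### The SAE definition has no criterion for other medically important events, so a convulsion or systemic hypersensitivity reaction outside its four outcomes needs no causality rating, ethics committee SAE report or annual list entry

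*Protocol*

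**What the plan says.** Protocol section 8.2.1 introduces its definition with "Serious adverse events are those which result in" and lists four items: death; "A life-threatening event (i.e. an immediate risk of death"; "Hospitalization or prolongation of hospitalization"; and severe or permanent disability. No item covers other medically important events. Neither document lists events that always count as serious.

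Later steps depend on that definition:

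- Causality (8.2.1): "The investigator will decide whether the SAE is related to the treatment". No rating is asked for non-serious events.
- Reporting (8.2.1): SAEs go from investigator to sponsor without undue delay, and from sponsor to the METC within 7 days if fatal or life-threatening and within 15 days otherwise.
- SUSARs (8.2.2): the first of three conditions is "the event must be serious (see chapter 8.2.1"; the third is that the reaction is unexpected against the product information.
- Annual safety report (8.3): its first part is "a list of all suspected (unexpected or expected) serious adverse reactions" with a summary table. Its second part is a full safety analysis with a benefit-harm evaluation, not limited to serious events.

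Section 7.4 gives among the known harms "increased blood pressure with rarely convulsions and hypersensitivity reactions". The Summary and section 7.3 name the same harms, and 7.3 refers to the SPC for them. On the setting of dosing, section 5.2 says: "Treatment is administered during weekly home visits after discharge from the LUMC".

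**The concern.** Two of the harms the protocol names for its own product can occur in a form that meets none of the four outcomes. With most doses given at home, an infant could have a short convulsion or a systemic reaction, recover, and not be admitted. By rule that event is non-serious, and no one has to record a view on whether the drug caused it.

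This is off-label use in newborns, and the Summary says the known risks were observed in other populations. The SAP plans 22 infants per arm, so one such event is a material share of the safety information on darbepoetin that the trial can produce. The analysis plan does not make up for it: the SAP safety end points (4.3) are systolic blood pressure and ferritin only, and its table shells have no row for adverse events. A causality opinion not recorded at the time is hard to reconstruct later.

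**Working it through.** The plan states no figure on this point and no arithmetic applies. The check takes one event through the definition and then through each reporting route.

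**Step 1. Is the event serious?** Take a convulsion or systemic hypersensitivity reaction with no immediate risk of death, no severe or permanent disability, and no admission caused or prolonged. It meets 0 of the 4 criteria in 8.2.1, so it is non-serious. Admission alone does not decide this:

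- an event at home with an immediate risk of death meets the second criterion;
- one that leaves severe disability meets the fourth;
- one that extends the initial stay meets the third.

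The gap is only what remains outside all four.

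**Step 2. Which routes does that event reach?**

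| Route | Trigger in the documents | As written | If it counted as serious |
|---|---|---|---|
| Recording (8.2.1) | any AE reported or observed | yes | yes |
| Follow-up (8.4) | any AE | yes | yes |
| DSMB (8.6; SAP 4.2.1) | AEs and SAEs | yes | yes |
| Annual safety analysis (8.3, second part) | not limited to serious events | open | open |
| Section 10 notice (8.1) | disadvantages may be significantly greater than foreseen; no seriousness threshold | open | open |
| Causality rating (8.2.1) | SAE | not required | required |
| Report to sponsor, then METC within 15 days (8.2.1) | SAE, expected or not | no | yes |
| Annual list and table (8.3, first part) | serious and suspected to be a reaction | no | yes, if suspected |
| 48-hour notice (8.2.1) | death, life-threatening SAE or unexpected SAE | no | only if unexpected, since the event is not life-threatening |
| SUSAR (8.2.2) | serious, suspected and unexpected | no | only if suspected and unexpected |

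**Step 3. What does the missing criterion cost?** Rows whose outcome changes for a typical case are the causality rating, the SAE report to sponsor and METC, and the annual list and table. For the last two rows seriousness is not the only barrier. Section 7.3 refers to the SPC for these reactions, so a typical case would probably be expected. Those rows change only for a case whose nature or severity departs from the SPC.

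**The case against.** The strongest reply is that the event is far from invisible. It is recorded and followed until it abates or is stable. It goes to a DSMB that can review individual records for associations with the study protocol, receives safety data unblinded, meets at least yearly, and can be called to extra meetings. The annual safety analysis is not confined to serious events, and section 8.1 has no seriousness threshold. The documents do not contradict themselves here and quote no standard that demands a fifth criterion. The Summary calls the risks small.

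All of that stands, and it rules out several stronger readings:

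- A reader might infer that any such event without admission is non-serious. The life-threatening and disability criteria need no admission, and prolonging an existing stay also counts.
- A reader might infer that the event is absent from the annual safety report, or reaches nobody but the DSMB. It misses the list and table of serious reactions; the safety analysis and the section 8.1 notice remain open.
- A reader might infer that the definition is what blocks the 48-hour notice and SUSAR reporting. For typical cases expectedness would probably block both anyway.
- A reader might attach a probability. With an assumed risk r per infant, the chance of at least one event in 22 is 1 − (1 − r)^22: 20% at r = 1% and 90% at r = 10%. The documents give no r, so these figures only restate the assumption.

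The open routes do not replace the missing ones. None requires a causality rating. The DSMB looks at individual records only as needed, and its advice goes to the principal investigators, reaching the METC only if they do not follow it in full. The protocol does not say what adverse event content the annual analysis must have. The section 8.1 notice turns on harm beyond what was foreseen, and these harms were foreseen.

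**Conclusion.** The point holds in a limited form. The definition is a stated, closed rule, and it classes some presentations of two named harms as non-serious. For those presentations three things are lost: the required causality rating, the SAE report to the METC within 15 days, and the entry in the annual list and table where a reaction is suspected.

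No magnitude can be given, because the documents contain no event rate and do not say how often such events would be managed without admission. The conclusion rests on reading the four criteria as exhaustive, as section 8.2.1 presents them, and on typical cases being expected under the SPC. The SPC, DSMB charter and monitoring plan are separate documents and were not available; the charter or plan could contain rules that narrow the gap. No efficacy estimate or error rate is affected. The change is worth making because it is cheap and the safety data in this trial will be few.

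**What to change.** Add a fifth criterion to Protocol section 8.2.1, identical in both arms: *any other event considered medically important by the investigator, including any convulsion or systemic hypersensitivity reaction, whether or not the infant is admitted*. Naming the two events removes discretion for them, which helps in an open-label trial; using the same rule in both arms keeps SAE counts comparable.

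The causality rating, the report to sponsor and METC, and (for suspected reactions) the annual list and table then follow from the existing text. The 48-hour notice will apply only if the event is also unexpected or life-threatening, and SUSAR reporting only if it is also suspected and unexpected. The amendment should not claim more than that.

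The cost is one line in the protocol, a matching line on the SAE form, and a few more SAE reports in a trial of 44 infants. No extra visit, test or procedure is needed.
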